Table 1. Specific Aims of the Kids FACE FEARS Trial

Aim	Domain	Objective
Aim I	Comparative Effectiveness	To compare the acute and longer-term effectiveness of Therapist-Led CBT (telehealth, office-based, or hybrid) versus Guided Online CBT (with minimal clinician involvement) for treating youth anxiety identified in pediatric healthcare.
Aim II	Heterogeneity of Treatment Effects	To determine whether key factors predict or moderate differential treatment engagement or response, in turn informing treatment personalization for various patient subgroups.
Aim III	Implementation Facilitators and Barriers	To explore quantitative and qualitative data to understand perspectives, preferences, background factors, clinical and treatment engagement variables, and organizational factors that impede or facilitate implementation of, and patient engagement with, the comparators in pediatric health settings.

Note: Kids FACE FEARS=Kids Formats of Anxiety Care Effectiveness study For Extending the Acceptability and Reach of Services

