4.1 Primary Objective

The objective of Aim 1 (*Comparative Effectiveness*) is to compare the acute and long-term effectiveness of Therapist-Led CBT (telehealth, office-based, or hybrid) vs Guided Online CBT (with minimal clinician support) for treating youth anxiety identified in pediatric healthcare. It is hypothesized that youth in both conditions would show significant curvilinear improvements over time characterized by relatively steep improvements during the beginning and middle of the treatment phase, followed by a slowing down of improvements toward the end of treatment and then relative stability across the follow-up time interval. Comparative effectiveness analyses will

compare differences in outcome slopes across the two conditions. Aim 1 focuses on the following primary treatment outcomes across the comparators: family-rated anxiety severity, family-rated anxiety-related life impairment, independently rated treatment responder and anxiety remission status, family perceived effectiveness, and family satisfaction with care. Data on a range of secondary outcomes are also collected.

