7.16 Statistical Considerations

Study results will be reported according to CONSORT guidelines.

7.16.1 Sample size determination. Power analysis to determine the appropriate sample size for the trial had to take into account data clustering and repeated measurements. Study data were clustered in multiple ways, resulting in non-independent observations and inflated type I error. First, there were multiple observations per child due to the repeated measures design with four major assessment points. Second, there was additional clustering due to multiple children from each site. The intraclass correlation (ICC) is a quantitative estimate of clustering and allows for adjustment for non-independence. Study investigators estimated an ICC of .5, meaning it was anticipated that 50% of the variation in the observations would be due to differences between individuals and between sites (the remaining 50% of the variation was assumed to be due to individuals varying in their responses over time). The design effect (DE) reflects the extent to which standard errors are deflated if clustering is ignored. The DE is equal to $1 + (m - 1) \times \text{ICC}$, where m is the number of repeated measures. Accordingly, with 4 time points and an assumed ICC of .5, the design effect was calculated to be 2.5. Any sample size estimate must be multiplied by 2.5 in order to obtain a sample size appropriate for the observed clustering while maintaining nominal alpha and power levels.

The required study sample size was calculated via conventional methods for repeated measures / mixed models analysis. Required sample size is a function of the alpha (type I error rate) and beta (1 – power) values. Required size per group is: $n = 2 * (Z_{1-\alpha} + Z_{1-\beta})^2$. Before adjusting for the DE, these computations found $n=60$ was required in each group for an $\alpha=.05$ (assuming family-wise error rates=.05 across the study to account for multiple comparisons) and $\text{power}=.8$ (corresponding to $\beta=.2$). After adjusting for the DE of 2.5, this power analysis indicated $n=150$ was required per group (60×2.5), for a total of $N = 300$.

The needed sample size of $N = 300$ (outlined above) was based on the primary comparative effectiveness tests of this study (Aim I). That said, a sensitivity analysis was also conducted to evaluate the magnitude of effects that could be detected in moderation analyses

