7.16.3 Covariates

Covariates for each model will include site, language of care, youth age, youth gender, youth race, youth ethnicity, and family resource insecurity (see Measures)

7.16.4 Primary analyses: Comparative effectiveness analyses. For primary analyses on continuous outcomes that were measured across the 4 major timepoints (e.g., caregiver- and youth-reports on the PROMIS Anxiety Scale, CALIS), mixed models of change¹⁴⁴ will be run separately for each outcome. Mixed models are preferred for longitudinal designs because they allow for individual estimates of change and have robust power in the presence of missing data and attrition.^{145,146} Covariates for each model will include site, language of care, youth age, youth gender, youth race, youth ethnicity, and family resource insecurity (see Measures), and any other baseline variables found to significantly differ across participants in the two conditions. The random effects of intercept (reflecting individual variation in mean outcome level) will be assessed. The fixed effects of Treatment Condition, Time, and the Treatment \times Time interaction will be analyzed in the prediction of change. We will examine non-linear models of change (i.e., log transformations of Time), which afford examination of symptom trajectories across time that are not gradual and incremental (e.g., steep improvements during initial weeks of treatment, followed by a slowing down of improvements toward the end of treatment, and then relative stability across the follow-up time interval). To aid interpretation of the meaningfulness of between-group differences, Cohen's d 's will be computed for each continuous outcome on model means at post and follow-up.

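### For PROMIS and CALIS, the single Treatment × Time slope does not give separate acute and longer-term estimates; supportive visit-specific estimates at posttreatment and Week 52 should be added

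*Combined protocol and SAP*

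**What the plan says.** Table 1 (section 4) sets the purpose of Aim I: "To compare the acute and longer-term effectiveness of Therapist-Led CBT" with Guided Online CBT. Section 4.1 says that the analyses will "compare differences in outcome slopes across the two conditions". It expects both arms to improve steeply, then slow, then show "relative stability across the follow-up time interval".

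For continuous outcomes measured at all four assessments (PROMIS Anxiety and CALIS, caregiver and youth report), section 7.16.4 fits one mixed model per outcome with Treatment, Time and one Treatment × Time term. On the shape of Time it says "We will examine non-linear models of change (i.e., log transformations of Time"). Section 7.16.5 refers back to log time as the form entered for Aim I, so log time is the natural reading. The unit of Time (weeks or visit number) is not stated.

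Section 7.16.4 adds that Cohen's d "will be computed for each continuous outcome on model means at post and follow-up". It gives no confidence interval or test for these values. The only random effect named is the intercept: "The random effects of intercept (reflecting individual variation in mean outcome level) will be assessed".

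PARS response and satisfaction have their own posttreatment models and are not affected.

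**The concern.** Aim I contains two questions: is there a difference at the end of treatment, and is there one at a year? A model with one slope has two treatment parameters, a level and a slope, with which to describe arm differences at four visits. Posttreatment and Week 52 values taken from it share those parameters, so each is partly determined by what happens at the other visit.

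If an arm difference present at the end of treatment fades by Week 52, the slope can be near zero and an acute difference can be missed. If a difference appears only after treatment, the fitted curve shows part of it at posttreatment. The planned output would not show the reader that either had happened.

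**Working it through.** **Inputs from the plan.** 150 per arm and "Study investigators estimated an ICC of .5" (section 7.16.1); assessments at Weeks 0, 8, 20 and 52, the latest mid- and posttreatment times (section 7.1); 30–50% attrition by the last follow-up (section 7.15.4). The plan's design effect reproduces: 1 + (4 − 1) × 0.5 = 2.5, and 60 × 2.5 = 150. The plan gives no figure for the slope test itself, and its printed sample-size formula contains no effect size.

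**Assumptions.** Time coded log(week+1), two-sided .05, SD units, equal correlations of .5, complete data, posttreatment at Week 20. The true patterns are illustrations.

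**Fitted curve.** t = 0, 2.197, 3.045, 3.970; mean 2.303; Sxx = 8.645. With balanced data and equal correlations, the fitted arm difference at time t is d̄ + b(t − 2.303), where b = Σ(t − 2.303)d / 8.645.

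- SE(b) = √[(2/150)(1 − 0.5)/8.645] = 0.0278.
- Var(d̄) = (2/150)(1 + 3 × 0.5)/4 = 0.00833.

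**Dependence of the two planned values.** Posttreatment and Week 52 lie 0.742 and 1.667 above the mean of t, and SE(b)² = 0.000771.

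- Covariance: 0.00833 + 0.000771 × 0.742 × 1.667 = 0.00929.
- Variances: 0.00833 + 0.000771 × 0.742² = 0.00876, and 0.00833 + 0.000771 × 1.667² = 0.01048.
- Correlation: 0.00929/√(0.00876 × 0.01048) = 0.97. For visit-specific differences it is 0.5.

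**Model means under assumed patterns.**

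| True difference, Weeks 0/8/20/52 | Fitted post | Fitted Week 52 | z for slope | Slope power |
|---|---|---|---|---|
| Held: 0/.3/.4/.4 | 0.355 | 0.455 | 3.88 | 97% |
| Partly fading: 0/.3/.4/.2 | 0.276 | 0.340 | 2.49 | 70% |
| Vanishing: 0/.3/.4/0 | 0.198 | 0.226 | 1.10 | 20% |
| Late-only: 0/0/0/.4 | 0.157 | 0.229 | 2.78 | 79% |

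Example, vanishing: d̄ = 0.175. b = [0.3 × (−0.106) + 0.4 × 0.742]/8.645 = 0.0306. Fitted post = 0.175 + 0.0306 × 0.742 = 0.198, and z = 0.0306/0.0278 = 1.10.

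**Visit contrast.** The Week 20 change contrast has SE √[(2/150) × 2 × (1 − 0.5)] = 0.1155, so 0.4 gives z = 3.46 and 93% power. With a common baseline mean the SE is √[(2/150)(1 − 0.25)] = 0.100, and power is 98%. Giving the slope model a common baseline mean as well raises its power in the vanishing case from 20% to 52%.

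**With attrition.** With 10/20/40% missing at Weeks 8/20/52, slope power is 95% (held) and 36% (vanishing), against 89% for the Week 20 contrast. With a common baseline mean in both, the vanishing case gives 65% against 95%.

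**The case against.** The strongest reply is that the slope is the stated comparison and that log time was chosen to match the stated hypothesis. This largely stands. The slope test is valid, and if the arm difference is sustained the planned means mislead little. No passage predicts a fading or late-only difference. However, the hypothesis describes the course within each arm. It does not say that the difference between arms follows the same curve, and whether a difference lasts is the longer-term half of Aim I.

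A reader might infer several stronger points that the documents do not support:

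- **That the plan has no posttreatment or follow-up estimates.** It has the Cohen's d values. The difficulty is where they come from.
- **That the planned values have a fixed Week 52/post ratio.** Under log(week+1) the ratio of arm differences in change from baseline is fixed at 3.970/3.045 = 1.30. The plan uses model means, and the Treatment main effect is free, so their ratio varies: 0.455/0.355 = 1.28 if held, 0.226/0.198 = 1.14 if vanishing.
- **That the model could give the wrong sign.** This comes from fitting linear weeks to a vanishing difference. Sections 7.16.4 and 7.16.5 together point to log time.
- **That a random intercept alone makes the test too liberal.** Its standard error is right under the plan's ICC of .5 with equal correlations, and the documents give no slope variance or decay in correlation.

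**Conclusion.** The point holds as a gap in what will be reported, and the planned test remains sound. For four outcomes (two measures, two informants), the planned posttreatment and Week 52 values are two readings of one curve and cannot answer the acute and longer-term questions separately. In the assumed cases the error in the planned means ranges from about 0.05 SD (held) to 0.20 SD at posttreatment and 0.23 SD at Week 52 (vanishing). The loss of power for an acute difference is serious only if that difference fades. These sizes rest on log(week+1), equal correlations of .5, posttreatment at Week 20 and the assumed patterns; other time codings or earlier completion would change them.

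A reader might also conclude that the visit contrasts should replace the slope or become eight confirmatory tests. That does not follow. Section 7.16.1 works from a single error budget ("assuming family-wise error rates=.05 across the study to account for multiple comparisons"), and dividing it further would be a trade-off, not a correction.

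**What to change.** 1. Keep the log-time slope as the confirmatory test and state its coding, for example log(week+1) with actual elapsed weeks.
2. For the same four outcomes, add a supportive model with visit as a 4-level factor, Treatment × visit, a common baseline mean or baseline adjustment, and unstructured within-child covariance. Report the posttreatment and Week 52 arm differences with 95% confidence intervals, and take Cohen's d from them.
3. Label these estimates supportive, so that the family-wise .05 is not split further.
4. Include visit-by-arm terms in the imputation model, so that imputation does not re-impose the fitted curve.
5. Report assessment timing by arm, with the log-time model on actual dates as the check. A random slope is an optional sensitivity analysis.

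**Cost.** SAP wording and one more model per outcome, in software that allows an unstructured covariance beside the named lme4. No new data are needed.

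**Precision.** With a common baseline mean, the 95% half-width is 1.96 × 0.100 = 0.20 SD with complete data. With 10% missing at Week 8, 20% at posttreatment and 30–50% at Week 52, it is 0.22 SD at posttreatment and 0.23–0.27 SD at Week 52. If the difference really is log-linear (0/.22/.31/.40), the posttreatment contrast has 77% power against 95% for the slope, or 87% against 99% with a common baseline mean in both.

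**Timing.** Posttreatment is assessed at completion or at Week 20 (section 7.1), and completion is 10 sessions in one arm and 4 support calls in the other (section 7.6.3), so elapsed time may differ by arm. If both arms improve 1 SD by Week 52 on log time (an assumption), assessing one arm at Week 10 and the other at Week 20 shifts the contrast by (ln 21 − ln 11)/ln 53 = 0.16 SD. This is why the timing report in step 5 is needed.

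### The PROMIS and CALIS models give each arm its own baseline mean and take Cohen's d on fitted levels: precision is lost, and about half of a chance baseline gap enters d

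*Combined protocol and SAP*

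**What the plan says.** Section 7.16.4 covers "continuous outcomes that were measured across the 4 major timepoints", naming caregiver and youth PROMIS and CALIS as examples. Baseline is one of those four timepoints, so it is a response in the model.

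- **Fixed effects:** "The fixed effects of Treatment Condition, Time, and the Treatment" by Time interaction. No constraint sets the arms equal at baseline.
- **Random effects:** "The random effects of intercept (reflecting individual variation in mean outcome level) will be assessed". No random slope is named.
- **Covariates:** "Covariates for each model will include site, language of care, youth age, youth gender, youth race, youth ethnicity, and family resource insecurity". The baseline outcome score is not listed. The section also admits "any other baseline variables found to significantly differ across participants in the two conditions".
- **Time:** "We will examine non-linear models of change (i.e., log transformations of Time").
- **Effect size:** Cohen's d "will be computed for each continuous outcome on model means at post and follow-up". The SD in the denominator is not named.

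Section 4.1 says that the Aim 1 analyses will "compare differences in outcome slopes across the two conditions". Section 7.5 stratifies randomization by region, language and age group, not by baseline anxiety.

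**The concern.** With time counted from baseline, the Treatment term is the fitted difference between arms before treatment starts. In randomized arms that difference is chance. Estimating it freely has two consequences.

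First, baseline information that has already been collected is not used to sharpen the arm contrast at posttreatment and follow-up.

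Second, the test and the effect size measure different things. Treatment by Time is a contrast in change. The d adds the Treatment term to the interaction, so it is a contrast in level. A chance gap at baseline pushes d one way and the slope the other. The plan offers d as its guide to whether a difference is meaningful, so a d and a p-value could diverge through imbalance alone.

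**Working it through.** **Inputs from the plan.** 150 per arm (synopsis, 6.3.1); ICC .5 with four timepoints (7.16.1); random intercept (7.16.4); 30-50% attrition by final follow-up (7.15.4).

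**Assumptions made here.** Total SD = 1; visits at Weeks 0, 8, 20 and 52 (section 7.1 gives Weeks 8 and 20 as the invitation points for families who have not yet finished, so actual times may be earlier); log time taken as log(1 + week); correlation ρ = .5, range .3 to .7; retention by visit of 1, .9, .8, .7 (30% dropout) or 1, .85, .7, .5 (50%).

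**The plan's own figure.** The design effect 1 + (4 − 1) × .5 = 2.5 and the step 60 × 2.5 = 150 reproduce. The 60 does not: the printed formula gives 2 × (1.96 + .842)² = 15.7 two-sided, or 12.4 one-sided, because no effect size or SD enters it. Nothing below depends on the 60.

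**Step 1: size of a chance baseline gap.** SE = √(2/150) = .1155 SD. The 95% limit is 1.96 × .1155 = .226 SD.

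**Step 2: share of the gap that enters d.** With categorical time the share is ρ. With log time it is ρ + (1 − ρ)h, where h is the weight of the baseline row in the fitted value at that visit: h = .0525 at Week 20 and −.194 at Week 52.

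| ρ = .5 | Share | 1-SE gap moves d by | 95%-limit gap moves d by |
|---|---|---|---|
| Post, log time | .5 + .5 × .0525 = .526 | .061 | .119 |
| Follow-up, log time | .5 + .5 × (−.194) = .403 | .047 | .091 |
| Either visit, categorical | .500 | .058 | .113 |

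Over ρ = .3 to .7 the log-time share is .34 to .72 at post and .16 to .64 at follow-up. A null simulation of 4,000 replicates (log time, ρ = .5) gave .53 and .41, about .01 with a common baseline, and a mean arm difference of about 0. The slope moves the opposite way: baseline has weight −.266 in the fitted log-time slope, so the coefficient on the gap is .5 × (−.266) = −.133.

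**Step 3: precision, categorical time, complete data.** With free baselines, the variance of the level contrast is 2/150 = .01333 (SE .1155). With a common baseline it is (2/150)(1 − ρ²) = .0100 (SE .1000), a 25% cut. The free-baseline model would need 150/.75 = 200 per arm to match. The ratio 1 − ρ² is .91, .75 and .51 at ρ = .3, .5 and .7, so the cut runs from 9% to 49%. Measured against the change contrast, whose variance is (2/150) × 2(1 − ρ), the ratio is (1 + ρ)/2, which is also .75 at ρ = .5.

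With dropout at ρ = .5 the ratios are .79 (post) and .81 (follow-up) for 30%, and .81 and .85 for 50%: cuts of about 15 to 21%. For illustration, at an assumed d of .30 with complete data, power is Φ(.30/.1155 − 1.96) = 74% against Φ(.30/.1000 − 1.96) = 85%.

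**Step 4: log time.** At ρ = .5 with complete data, a common baseline takes the SE of the slope from .0278 to .0227 (variance ratio .67). The level contrast goes from .0936 to .0692 at post and from .1024 to .0903 at follow-up. Part of this comes from curve shape. With no baseline difference and a single Treatment by log-Time term, the arm difference is a line through zero: .0692/.0903 = .77 = ln 21/ln 53. Post and follow-up are then one parameter rescaled. If the true differences at the four visits were 0, .2, .3 and .1, the fitted post d would be .15, against .18 under the plan's model and a truth of .30. At follow-up it would be .20 against .22, with a truth of .10.

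**The case against.** A Treatment by Time mixed model with free baselines is conventional and valid. Sections 7.16.2.2 and 7.16.2.4 commit to intention-to-treat, and the estimator is unbiased over repeated randomizations. The Aim 1 slope test already works relative to each arm's own baseline, and d is an aid to interpretation. All of that stands. It makes this a matter of efficiency and reporting, not of validity.

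Three stronger readings are tempting, and the documents do not support them:

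- *That randomization is set aside.* It is not. Randomized arms are compared as randomized; only the implied equality of expected baselines goes unused.
- *That the whole baseline gap is reported as effect.* Under the planned random intercept only 0.40 to 0.53 of it is, at ρ = .5.
- *That a one-third gain is available.* The 33% cut for the log-time slope is a favourable case: complete data, a random intercept only and an exact log(1 + week) shape. The planning ICC also includes between-site variation, while site is already a covariate, and entry requires a PROMIS T-score of at least 55. Both could lower the residual correlation, so .3 is a plausible low case (9% for the level contrast).

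The clause admitting baseline variables that differ significantly is not an answer. It depends on the data, misses non-significant gaps, and would make the baseline score a covariate while it is still an outcome row.

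**Conclusion.** The point holds as a free improvement. The planned PROMIS and CALIS comparison is sound but less precise than the collected data allow, and its test and effect size are different quantities. At ρ = .5 and 150 per arm, chance imbalance typically moves d by about .05 to .06 and by about .09 to .12 at the 95% limit. The cleaner precision figure is the categorical one: 25% of variance with complete data, and about 15 to 21% under the attrition that the plan expects. These sizes rest on the planning correlation, compound symmetry and the assumed visit times and retention patterns. The direction does not depend on the exact correlation within the range examined.

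**What to change.** For caregiver and youth PROMIS and CALIS, prespecify one of two models:

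- a constrained longitudinal model with a baseline mean common to both arms, categorical visit, and separate Treatment contrasts at midtreatment, posttreatment and follow-up; or
- a model of post-baseline rows only, with the baseline score as a prespecified covariate.

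Take both the test and Cohen's d at posttreatment and follow-up from the same baseline-adjusted arm contrast, with the pooled baseline SD as the stated denominator. Do not pair the common baseline with a single Treatment by log-Time term for these contrasts, for the reason shown in Step 4. A log-time slope model can stay as a supporting description of trajectory; sections 4.1 and 7.16.4 should then name the same primary contrast.

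The cost is SAP wording and a few more model parameters. No new data are needed, and the constrained model can be fitted in the planned lme4 software. Because the Aim II models build on these, settle the specification before either set is run.
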